### 5.3. Method for Assigning Participants to Treatment Groups

Participants will be randomly assigned to one of two treatment conditions: Bupropion 300 mg/day (n = 180) or placebo (n = 180). We will use small-block randomization by site (Penn or MATER) provided by [name], the study biostatistician. A PHQ-9 score of 10 or greater will be used to identify major depression and stratify the randomization on it. Study site (Penn or MATER) will be the second of the two stratification variables. Study staff and the Investigational Drug Service (IDS) staff will be responsible for medication randomization. The process for randomization is: 1) The research coordinator will complete a “randomization form,” which includes the variables to be entered into the randomization program and fax or email the form without protected health information to the UPenn site; 2) A designated study staff member

Table 1: Medication Dispensing Schedule

	Medication Dispensed For	Morning Dose	Evening Dose	Total Daily Dose
Visit A: Screening	N/A	No medication	No medication	
Visit B: Baseline	Wk 1	150 mg	No medication (for first 3 days); then 150 mg	150 mg
Visit C: Wk 1	Wk 2 through Wk 5	150 mg	150 mg	300 mg
Visit D: Wk 3	N/A	N/A	N/A	N/A
Visit E: Wk 5	Wk 6 through Wk 10	150 mg	150 mg	300 mg
Visit F: Wk 7		150 mg	150 mg	300 mg
Visit G: Wk 10	Endpoint	No medication	No medication	N/A

CONFIDENTIAL

This material is the property of the University of Pennsylvania. Do not disclose or use except as authorized in writing by the study sponsor

Visit H: Wk 24 Post-TQD	N/A	No medication	No medication	N/A
Visit I: 2 wk postpartum	N/A	No medication	No medication	N/A
Visit J: 6 wk postpartum	N/A	No medication	No medication	N/A

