## 7. Statistical Plan

### 7.1. Power

A power analysis is provided only for the primary aims because the exploratory aim is hypothesis generating. Most of our power calculations were approximated as 2-sided t- or z-tests, with  $\alpha = 0.05$ , using PASS Software (Power and Sample Size, NCSS Software, Kaysville, UT). Equivalence testing was approximated as two one-sided tests, with  $\alpha = 0.025$  each.

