#### 7.1.1. Aim 1:

The primary efficacy analysis (**H1**) is a comparison in week 10 (of treatment) and week 24 post-TQD of CO-confirmed 7-day point prevalence quit rates for the placebo and bupropion groups. For the week-10 comparison, we expect that the quit rates in the placebo and bupropion arms would approximate those reported in bupropion trials in the general population of smokers (i.e., placebo = 21.2%; bupropion = 35.9%, OR = 2.1; ref. 44). A sample of 360 provides 88% power to detect a significant between-group effect. The OR for bupropion treatment is similar at 24 weeks, based on Jorenby et al. (168) and our own data, and results from 10 and 24 weeks are highly correlated ( $\rho > 0.7$ ). Thus, we have 80% power to detect a significant difference between treatment arms.

Safety analyses (**H2**) will examine maternal safety across the 10-week treatment and 24-week follow-up periods and fetal and birth outcomes. Key maternal and fetal outcomes to be compared across treatment groups include rates of moderate-to-severe side AEs of bupropion (from the AE checklist). Key birth outcomes will include Apgar scores, birth weight, duration of pregnancy, rate of obstetrical complications, and need for NICU admission. These analyses will involve a test of equivalence because we cannot use standard statistical tests to conclude that a non-significant comparison shows that the drug is safe (i.e., "the absence of evidence is not evidence of its absence"). In our past study with bupropion, 45% of bupropion-treated participants reported no moderate-to-severe AEs, vs. 47% of participants on placebo, a 2% difference. With the present sample size, we will have 82% power to detect similar equivalence between treatment arms on the frequency of moderate-to-severe AEs over the course of the trial, given that AEs are not significantly different between treatment arms, using an equivalence window of 0.30 to 0.60. Likewise, Oncken et al. (47) reported 38% AEs for the placebo group

CONFIDENTIAL

and 25% in the nicotine group. An equivalence test with placebo and bupropion groups both at 30% and an equivalence window for bupropion of +/-15% provides 81% power.

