## **7.2. Statistical Analyses**

[name] will oversee analyses, which will be conducted using Stata, SAS, or R-Language software. Preliminary analyses will assess sample characteristics (e.g., dependence, race) by treatment using t-test or contingency table methods. These variables will also be examined for their relationship to completion of outcome assessments. Variables related to treatment arm or completion of follow ups will be included as covariates in analyses of study aims. Compliance measures will be evaluated across treatment arms, and controlled for in primary analyses. We will examine the correlation between self-report and pill count data and week-5 bupropion plasma levels. We will use intent-to-treat as the primary method to evaluate study aims.

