### **7.2.1. Missing Data:**

We will examine whether the rate of missing data, primarily our smoking cessation outcome data, is related to a range of potential variables, including treatment arm allocation, and demographic and smoking-related variables. Standard bivariate statistical methods will be used to identify correlates of missing data. Variables associated with the rate of missing data ( $p < 0.05$ ) will be included as covariates in the analyses of aims. Items missing at random from assessments will be imputed prior to calculating final scores using conditional means, estimated with an iterated version of Buck's method (173). We will aim to avoid dropout and missed sessions by keeping participants connected to the trial and motivated to complete measures. In our clinical trials, close monitoring of participants and the use of incentives to offset travel costs have resulted in adherence and retention rates >80% (52). Primary analyses will assume that all participants for whom smoking outcome data are unavailable are smokers (intent-to-treat), which is conventional in smoking cessation research. Because this assumption can attenuate the differences between study groups in quit rates, we will also conduct a "completers-only" analysis, as done previously (174).

CONFIDENTIAL

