### **7.2.3. Specific Aim 2: Assess changes in depression symptoms and craving as mediators of bupropion's effect on quit rates.**

We will use a regression-based path model approach to examine mediation of treatment effects based on MacKinnon et al. (175). All variables will be standardized for the analyses. The two suspected mediators will be entered as standardized pre-post differences, continuously distributed and treated as normal in linear regression. The effects of treatment arm on

CONFIDENTIAL

mediators, and of mediators on outcome, will be assessed using linear regression and standardized variables. We will focus on changes in mediators from baseline to week 3, since abstinence-induced withdrawal effects typically peak within the first 3 weeks of cessation (174), but we can examine delayed changes to weeks 5, 7, and 10 as well. Assuming that treatment predicts our mediators, we will then assemble the path model using standard structural equation modeling approaches. The path model partitions the effect of treatment on outcome into direct (and unexplained) effects vs. mediated effects. We will then test the overall mediation hypothesis using the proportion of treatment effect explained (171-172), and the strength of each mediating pathway. To do this, we will estimate the model for standardized treatment predicting abstinence without mediators to estimate the direct effect of treatment in the unadjusted model ( $\hat{\beta}^{\dagger}$ ). We will then test whether treatment predicts each of the suspected mediators and, in turn, test whether mediators predict abstinence in an adjusted treatment model and estimate the effect of treatment in the mediator adjusted model  $\hat{\beta}^*$ . Finally, we will calculate the proportion of treatment effect explained, which is calculated as  $(\hat{\beta}^{\dagger} / \hat{\beta}^*)$ ; the standard error for this quantity is calculated using the delta method, and the mediation hypothesis will be tested using a z-test. Individual pathways will be tested using products of the coefficients along each path using a delta-method based z-test.

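### Aim 2 does not require the same women in the unadjusted and mediator-adjusted models, so wholly missed PHQ-9 or QSU assessments can bias the proportion of treatment effect explained

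*Combined protocol and SAP*

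**What the plan says.** Section 7.2.3 enters the two mediators, depression (PHQ-9) and craving (QSU), as standardised pre-post differences. For the overall mediation test the plan will "estimate the model for standardized treatment predicting abstinence without mediators to estimate the direct effect of treatment in the unadjusted model", then fit a mediator-adjusted model and form a ratio of the two treatment coefficients, with a delta-method standard error and a z-test. No sample is named for either model. Single pathways are tested separately by products of coefficients.

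Three other statements decide who would enter each model:

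- Section 7.2: "We will use intent-to-treat as the primary method to evaluate study aims".
- Section 7.2.1, on outcomes: "Primary analyses will assume that all participants for whom smoking outcome data are unavailable are smokers".
- Section 7.2.1, on scales: "Items missing at random from assessments will be imputed prior to calculating final scores using conditional means". This covers gaps within a completed assessment. No rule is given for an assessment that was missed altogether.

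Section 7.3 points elsewhere: it limits the analysis to women who complied with the protocol. Section 7.1.2 powers Aim 2 on all 360 women, with no allowance for missing mediators.

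**The concern.** A proportion explained is meaningful only if adding the mediators is the sole difference between the two models. Under the plan's rules, every randomised woman has an outcome for the unadjusted model. A woman with no follow-up PHQ-9 or QSU has no change score, and ordinary regression software would drop her from the adjusted model without comment. If she was also lost at the endpoint, she was scored a smoker. The adjusted model would then lose treatment failures selectively, and its treatment coefficient would move even if nothing were mediated.

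Section 7.2.1 itself notes that counting missing outcomes as smoking can shrink the difference between arms. Here that shrinkage could affect one coefficient and not the other. With equal loss in the arms, real mediation would look smaller or negative. With loss much heavier on placebo, mediation could appear where there is none. Section 7.1 treats Aim 2 as one of the powered aims, so its overall test deserves a defined sample.

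**Working it through.** **Inputs.** Section 7.1.1 gives the week-10 quit rates: "placebo = 21.2%; bupropion = 35.9%, OR = 2.1; ref. 44". Section 5.3 allocates 180 women to each arm. The missing shares are assumptions.

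**The plan's own figure.** Section 7.1.1 states: "A sample of 360 provides 88% power to detect a significant between-group effect". With 180 per arm and two-sided 0.05:

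- Pooled rate 0.2855; standard error under the null √(2 × 0.2855 × 0.7145 / 180) = 0.0476.
- Standard error under the alternative √((0.212 × 0.788 + 0.359 × 0.641) / 180) = 0.0470.
- z = (0.147 - 1.96 × 0.0476) / 0.0470 = 1.14, so power is 87.3%, in line with 88%.

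This confirms the inputs. Aim 2 states no proportion explained to reproduce.

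**Unadjusted coefficient, all 360 women.** Standardised coefficient = risk difference × SD(arm) / SD(outcome) = 0.147 × 0.500 / 0.4517 = 0.1627.

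**Adjusted coefficient with no true mediation, women with the mediator only.** Upper-end assumption: every woman without the mediator is scored a smoker. The quit rate among the remaining women is then p / (1 - missing share). With no mediation, adjustment changes nothing further, so the coefficient is the same formula in the reduced sample.

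**Share explained** = 1 - adjusted / unadjusted. This replaces the ratio printed in section 7.2.3 (unadjusted over adjusted), which equals 1 rather than 0 when nothing is mediated.

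| Missing, placebo / bupropion | Quit rates in remaining women | Risk difference | SD(arm) | SD(outcome) | Coefficient | Share explained, truth 0 |
|---|---|---|---|---|---|---|
| 5% / 5% | 22.3% / 37.8% | 0.155 | 0.500 | 0.458 | 0.169 | -4% |
| 10% / 10% | 23.6% / 39.9% | 0.163 | 0.500 | 0.465 | 0.175 | -8% |
| 20% / 20% | 26.5% / 44.9% | 0.184 | 0.500 | 0.479 | 0.192 | -18% |
| 15% / 25% | 24.9% / 47.9% | 0.229 | 0.499 | 0.479 | 0.239 | -47% |
| 25% / 20% | 28.3% / 44.9% | 0.166 | 0.500 | 0.482 | 0.172 | -6% |
| 25% / 10% | 28.3% / 39.9% | 0.116 | 0.498 | 0.476 | 0.122 | +25% |

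**Where the sign changes.** With 20% missing on bupropion, set placebo missing at 27.2%. The placebo rate is 0.212 / 0.728 = 0.291, the risk difference 0.449 - 0.291 = 0.158, SD(arm) 0.499 and SD(outcome) 0.484. The coefficient is 0.163, equal to the unadjusted value. Placebo loss must exceed about 27% before false positive mediation appears.

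**Relaxing the assumption, 20% missing per arm.** If women without the mediator quit at half the rate of the others, the rate among the others is p / (0.8 + 0.5 × 0.2) = p / 0.9. That is the 10% row, so the reading is -8%. If they quit at the same rate, the divisor is 1 and the bias is zero.

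**Same-sample check.** In a simulation of 2 million records per scenario, fitting both models on the same women gave a share explained of zero, within simulation error, under no mediation in every retention pattern tried. Mixing the samples gave -18% at 20% missing per arm.

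**The case against.** **The two samples are not written into the plan.** A reader might infer that Aim 2 is designed to set all randomised women against completers. Section 7.2.3 names no sample. The split follows from sections 7.2 and 7.2.1 plus default software behaviour, and section 7.3 names a different population. A path model fitted by full-information likelihood could keep every woman, though the plan cites only conventional structural equation methods. A delta-method standard error for the ratio needs the covariance of the two coefficients, which sits most naturally with one dataset. All of this stands. It leaves the sample undefined; it does not establish a common one.

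**Not every mediation result is exposed.** The product-of-coefficients tests do not compare a mediator-free effect with an adjusted one, so it would be wrong to say that the whole Aim 2 conclusion rests on this comparison. This stands.

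**The sizes may be smaller.** The planned focus is week 3, a telephone contact (section 6.5). Women lost later keep their week-3 PHQ-9 and stay in both models. Section 6.11 asks women who stop treatment to complete all scheduled assessments, by telephone if needed. The retention above 80% in section 7.2.1 comes from earlier trials and is not a rate for the mediator visit. This also stands, and is why the table is an upper end. For craving, however, Table 2 lists no QSU at week 3, so a change score beyond week 1 must come from the in-person visits at week 5 or 10. At week 10, a woman who misses the visit entirely lacks the mediator and is scored a smoker at once.

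**Higher placebo dropout need not create mediation.** The 25% / 20% row, at -6%, shows that a modest excess does not. Only a wide gap does.

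**Conclusion.** The point holds as a gap in the specification with a material consequence if the plan's rules are followed literally. Section 7.2.3 does not tie the two coefficients to one set of women, and section 7.2.1 has no rule for a wholly missed mediator assessment. The resulting bias is confined to the proportion explained and its overall test.

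With equal loss, its upper-end size runs from -4% to -18% on the planned standardised scale for 5% to 20% missing per arm. It is -8% at 20% missing if women without the mediator quit at half the rate of the others, and zero if they quit at the same rate. Unequal loss can push it further either way: about +25% when placebo loses 25% and bupropion 10%, about -47% when the losses are 15% and 25%.

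These figures rest on the week-10 planning rates, on assumed missing shares, and on one minus adjusted over unadjusted in place of the printed ratio. The documents do not support reading them as the expected bias. The primary efficacy and safety analyses are not touched.

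**What to change.** In section 7.2.3, name one analysis set and one outcome rule for both Aim 2 models, and reconcile that set with section 7.3.

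- **Primary:** all randomised women in both models, with wholly missing PHQ-9 and QSU assessments handled by multiple imputation (from arm, baseline scores, other visits and smoking reports) or by full-information likelihood in the path model.
- **Sensitivity:** both models refitted in the women whose mediator was observed.
- **Rule:** never combine coefficients estimated on different sets.

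The same edit should state the proportion explained so that it is zero under no mediation, and say at which visit the craving change is measured, since Table 2 has no QSU at week 3.

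The cost is protocol wording and modest programming, with no change to sample size or visits. The primary analysis takes on a missing-at-random assumption for the mediators. The sensitivity analysis shows how far the result depends on the way missed assessments are handled, but it cannot test that assumption.

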### 1.1. Background

**Smoking During Pregnancy is a Major US Public Health Problem:** Smoking during pregnancy is a major modifiable cause of poor pregnancy and child health outcomes in the US (1, 2). Maternal smoking increases the risk of a number of serious adverse outcomes of pregnancy, including spontaneous abortion, placental complications, preterm delivery, and fetal and neonatal death. The most consistent adverse effect of smoking during pregnancy is low birth weight (LBW, i.e., <2500 g) (1, 24, 25), the risk of which doubles with maternal smoking (2). In turn, LBW (particularly very low birth weight, i.e., <1500 g), exponentially increases morbidity and mortality risk (3). In the US, maternal smoking is responsible for 30% of LBW babies, 10% of premature deliveries, and 5% of infant deaths (7). Fortunately, smoking cessation by 16 weeks gestation (9, 10), or as late as the third trimester (10), results in a near-normal birth weight infant. Reductions in smoking also increase birth weight (26). Despite these risks, the majority of women who are smoking at the time of their first prenatal visit continue to smoke, risk factors for which include being unmarried, less educated, heavier smokers (>1/2 pack per day), depressed, with partners who smoke (27-30).

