TQD: target quit date; PP: postpartum; ICF: informed consent form; HIPAA: Health Insurance Portability and Accountability Act; Assessments: X=in-person; X=MINI sections A through K will be administered. X=Only MINI section B (Suicidality) will be administered; X=in-person only; T=by telephone; C=chart review; SORT: Slosson Oral Reading Test; MINI: Mini-International Neuropsychiatric Interview; TLFB: Timeline Follow-back Interview for cigarettes smoked; NMR: nicotine-metabolite ratio; [CO]: carbon monoxide concentration; AEs: adverse events FTND: Fagerstrom Test for Nicotine Dependence; BISS: Body Image State Scale; PHQ-9: Patient Health Questionnaire-9; WEAQ: Weight Efficacy After taken Quitting survey; QSU: Questionnaire of Smoking Urges; MED-Q: medication group question; \*CO readings may also be at the time of delivery and at the time of the post-partum office visit

An in-person or telephone interview will be used to obtain background information for use as potential covariates and to assess the study's external validity [including smoking history (e.g., age at initiation, past use of nicotine treatments, current rate, menthol vs. regular tobacco, presence of other smokers in the home), obstetrical history to confirm and augment information obtained from review of the medical record (number of pregnancies, pregnancy outcomes), and medical and psychiatric history (with current medications extracted from the medical chart). Sessions in which the assessments are conducted by telephone, the telephone interview should be completed prior to the in-person visit.

Nicotine dependence severity will be assessed with the Fagerstrom Test for Nicotine Dependence, a validated 6-item measure (144). We will measure depression symptom score using the PHQ-9 (145) and will use a score of 10 or more to differentiate depressed and non-depressed women. This cut point will enable us to use depression as a stratification variable and potential mediator. Craving severity, which has been related to long-term cessation in cessation trials (147), will be measured with the 10-item brief Questionnaire of Smoking Urges (QSU; 146). The QSU contains 2 subscales (anticipation of reward, relief from negative affect).

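### Aim 2 pre-specifies no adjustment for baseline common causes of mediator change and abstinence, so the share of the drug effect attributed to craving or mood can be biased in either direction

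*Combined protocol and SAP*

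**What the plan says.** Section 7.2.3 builds the Aim 2 analysis in three steps: treatment predicting abstinence without mediators, treatment predicting each mediator, and mediators predicting abstinence with treatment in the model ("test whether mediators predict abstinence in an adjusted treatment model"). The effects of arm on "mediators, and of mediators on outcome, will be assessed using linear regression and standardized variables". On the form of the mediators: "The two suspected mediators will be entered as standardized pre-post differences". On testing: "Individual pathways will be tested using products of the coefficients along each path using a delta-method based z-test". Section 7.1.2 sets the level at 0.025 for each of the two pathways. Section 7.2.3 names no baseline covariate, no assumption about confounding and no sensitivity analysis.

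Two general rules apply to every aim. Section 7.2: "Variables related to treatment arm or completion of follow ups will be included as covariates in analyses of study aims". Section 7.2.1 adds that correlates of missing data (p < 0.05) "will be included as covariates in the analyses of aims". Section 7.2.2 also allows covariates against confounding, with daily smoking rate among its examples, but this is optional and written for the H1 model.

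Section 1.1 lists risk factors for continued smoking in pregnancy, including "being unmarried, less educated, heavier smokers (>1/2 pack per day), depressed, with partners who smoke", and later says that other smokers in the home undermine cessation. These factors are measured. Section 6.3 states: "Nicotine dependence severity will be assessed with the Fagerstrom Test for Nicotine Dependence, a validated 6-item measure". The same section collects current smoking rate and other smokers in the home as potential covariates. In the analysis plan, smokers in the home appear only as an Aim 3 moderator (7.2.4).

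**The concern.** Arm is randomised; change in craving or depression is not. The coefficient of mediator change on abstinence has a causal meaning only if the common causes of both are in the model. A baseline trait that shifts mediator change and also makes quitting harder creates an association between the two even if the mediator does nothing. Multiplied by a real drug effect on the mediator, that association becomes an apparent mediated pathway.

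The rules that reach Aim 2 do not target such traits. Under randomisation a strong common cause is related to arm only by chance. It is related to missing follow-up only if it also drives dropout.

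At stake is the conclusion on mechanism: whether bupropion works through mood or craving, and how much of its effect that explains. Aim 2 has its own power statement and is not the exploratory aim. No efficacy or safety conclusion depends on it.

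**Working it through.** **The plan's own figures.** Section 7.1.2 gives 80% power for a one-sample effect of 0.16 with N = 360. Here 0.16 × √360 = 3.036. At two-sided 0.05, power is Φ(3.036 − 1.960) = 85.9%; at the corrected 0.025 it is Φ(3.036 − 2.241) = 78.7%, so the figure matches the corrected level. For 0.35 SD with 180 per arm, 0.35/√(2/180) = 3.320, giving 86.0% at 0.025, so the stated 80% is conservative. Neither figure bears on confounding; 0.35 SD is used below as the drug effect on the mediator.

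**Inputs from the documents.** 180 per arm (5.3); quit rates 21.2% and 35.9% (7.1.1); mediator shift 0.35 SD and level 0.025 (7.1.2); linear regressions and delta-method product test (7.2.3).

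**Assumed inputs.** The documents give no confounder strengths. Let r_m be the correlation of a baseline factor with mediator change and r_y its correlation with quit liability. There is a partial anchor for r_y. Section 1.1 reports quit rates of 20%, 15% and 5% across rising bands of cigarettes per day. The step from 20% to 5% is −0.842 − (−1.645) = 0.80 probit units. If the bands span 2 to 3 SD of consumption (assumed), the slope is 0.40 to 0.27 per SD and r_y = slope/√(1 + slope²) = 0.37 to 0.26. Nothing in the documents anchors r_m.

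**Share falsely explained, closed form.** The true mediator effect is set to zero.

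- Total effect on the liability scale: Φ⁻¹(0.359) − Φ⁻¹(0.212) = −0.361 − (−0.800) = 0.438.
- One mediator: spurious coefficient b = r_m × r_y, and share = 0.35 × b / 0.438.
- Both mediators, each shifted 0.35 SD, each correlated r_m with the factor, and correlated 0.45 with each other (assumed): each b = r_m × r_y / 1.45, and combined share = 2 × 0.35 × b / 0.438.

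| r_m, r_y | One mediator | Both mediators |
|---|---|---|
| 0.2, 0.2 | 0.35 × 0.04 / 0.438 = 3.2% | 4.4% |
| 0.3, 0.3 | 0.35 × 0.09 / 0.438 = 7.2% | 9.9% |
| 0.4, 0.4 | 0.35 × 0.16 / 0.438 = 12.8% | 17.6% |

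Simulation of the planned linear models gives 6 to 12% (one mediator) and 9 to 17% (both) for correlations of 0.3 to 0.4, within about a point of the closed form. Share here means indirect over total effect. On the unadjusted-to-adjusted ratio printed in 7.2.3, a false share of 12.8% would show as 1/(1 − 0.128) = 1.15 instead of 1.

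**False rejection by the product test (simulation, two-sided 0.025).**

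- One mediator, no adjustment: 4.2% at 0.3/0.3 and 19.4% at 0.4/0.4.
- Both mediators in the model, no adjustment: about 1.3 to 4.5% per pathway. At 0.4/0.4 it is 4 to 6% as the correlation between mediators varies from 0.4 to 0.5.
- Factor added to both path equations: under 1% throughout.
- One mediator at 0.2/0.2: about 1% unadjusted.

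**Second parameterisation.** With a logistic outcome and one mediator, r = 0.3 and an odds ratio of 0.61 per SD give 3.4%. An odds ratio of 0.45 gives 11.7%. Weak confounding (r = 0.1, odds ratio 0.74) gives 0.2%.

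**Two boundary checks.** If treatment does not move the mediator, the product test rejects in about 0% of trials with or without the factor. If r_m = −0.3, the spurious indirect effect changes sign and the share is about −7%.

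**The case against.** A reader might infer that the Aim 2 models adjust for treatment alone. The documents do not support that. Sections 7.2 and 7.2.1 put covariates into the analyses of all aims, and 7.2.1 screens demographic and smoking-related variables against missingness. That rule is not inert. In the one-mediator 0.3/0.3 setting, assume 20% missing and a factor correlated 0.2 with missingness. The rule then admits the factor in 76% of trials and the error falls to 1.4%. At a correlation of 0.1 it is admitted in 26% (error 2.4%); at 0.3, in 98% (0.5%). Protection therefore depends on how far the confounder also predicts dropout, which nobody knows in advance.

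A path model may well hold depression and craving change together, and then the second mediator absorbs part of a shared cause. The per-pathway error of 1 to 5% lies around the nominal 2.5%, and part of the contrast with under 1% reflects the known conservatism of the product test. This stands, and it makes the one-mediator rejection rates an upper picture. It does not rescue the proportion explained, whose bias grows when both mediators are in the model.

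A reader might also infer that false mediation is the expected result. That goes too far. Section 1.1 links heavier smoking and smoking partners to continued smoking, not to change in PHQ-9 or QSU. If more dependent women start higher and fall further, the bias hides mediation. Spurious mediation also needs a real drug effect on the mediator, although that is the case the plan expects.

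**Conclusion.** The concern holds in a limited form. Section 7.2.3 commits to no adjustment for baseline common causes of mediator change and abstinence, and the general rules capture them only incidentally. If such a factor correlates 0.3 to 0.4 with both, the clearest effect is on the mediated share: about 6 to 12% with one mediator or 9 to 17% with both, when the truth is zero. The pathway test is clearly inflated only with one mediator in the model (about 4 to 20%).

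These sizes rest on assumed correlations, a 0.35 SD drug effect on the mediator, and an assumed correlation of about 0.45 between mediators. At 0.2 the distortion is small, and the sign is not known. It would be wrong to read this as a threat to the abstinence, adverse-event or birth-weight comparisons between randomised arms. It is a cheap improvement to a mechanistic aim.

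**What to change.** In 7.2.3, name one fixed set of baseline covariates and put it in the treatment-to-mediator, mediator-to-abstinence and total-effect models alike:

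- FTND score (Visit B)
- baseline cigarettes per day (30-day Timeline Follow-back, Visit A)
- number of smokers in the home (smoking history questionnaire, Visit B)
- site
- baseline PHQ-9 and baseline QSU
- education, if it is recorded under demographics; the documents do not name it among the items collected

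Apply the set whatever the arm-balance and missingness screens show. State whether the two mediators are modelled jointly. State that each pathway estimate assumes no other common cause of mediator change and abstinence. Report how strong an unmeasured common cause would have to be to bring the indirect effect to zero.

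The cost is SAP wording, about six or seven parameters and a little more analysis. At the planned rates there would be about 180 × (0.212 + 0.359) = 103 quitters among 360 women, which supports a model of that size. Apart from the check on education, no new data are needed. Fixing the list before unblinding also removes any choice of covariates after the results are seen.
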